15.2 PHARMACOKINETIC SAMPLE PROCESSING

Collection, Processing and Shipment of Plasma Specimens

Up to 2 blood specimens (approximately 0.5-1mL of blood per sample) for pharmacokinetic analysis will be collected during the study from each subject who receives study drug the following times relative to study drug administration:

- 24 hours (+6 hours) following initiation of study drug dosing (collected at least 2 hours after the last dose change)
- Immediately prior (within 1 hour) to beginning to down titrate (wean) study drug, or on Study Day 28 if the subject continued on IV Remodulin
 - A second sample will not be required in subjects who are unblinded and identified to be on placebo

Time and date of blood draws will be recorded. If any early or late blood draws are performed, the time and reason should be recorded in the eCRF.

Specimen Processing

- Collect approximately 0.5- 1mL blood specimen in a collection tube containing K3-EDTA or K2-EDTA as an anticoagulant and immediately place the specimen on ice.
- Within 1 hour of collection, centrifuge the specimen at 4°C for 10-15 minutes at 3000g.
- Label the shipping tube with the subject number, and specimen collection time and date.
- Pipette approximately 250µL plasma into a cryogenic storage tube. Pipette the remainder of the plasma into a second, identically labeled cryogenic storage tube for use as a backup specimen for storage at the clinical site.
- Freeze samples immediately at -70-80°C (-20 to -25°C permitted) until instructed to ship by Sponsor.

Shipping Procedures

- The sample will be transported on dry ice to the Sponsor-designated laboratory. The backup sample will be retained at the site and transported later in the event of an emergency or if deemed necessary by the Sponsor.
- All shipments must be accompanied by a packing list. Please note on the packing list any specimens that are hemolyzed.
- Package the shipping tubes to prevent breakage and contamination in Styrofoam boxes containing a generous supply of dry ice that will allow for 3 days in transit.
- Prior to the shipment of specimens, contact the Sponsor and the bioanalytical laboratory by phone and fax or email. An electronic copy of the packing list (manifest) should be provided to the laboratory in advance of the shipment.
- The bioanalytical lab shipping address and contact person will be provided prior to shipping of samples.

15.3 ADMINISTRATION OF REMODULIN

The preferred method of administration of Remodulin is by central venous access via an umbilical venous catheter (UVC) or peripherally inserted central catheter (PICC). Currently, there are no data to confirm whether Remodulin is compatible and may be administered in the same line/lumen with other IV administered agents; however, compatibility studies are planned. Therefore, one line or lumen must be dedicated solely to study drug when administering as a continuous IV infusion until the Investigator is notified by United Therapeutics of the outcome of the compatibility studies. Once compatibility with other IV agents has been confirmed, study drug may be administered in accordance with the data provided. It is recommended that an infusion set with a 0.22 or 0.2 micron pore size in-line filter should be used for IV administration, unless institutional policies and practices restrict use of in-line filters in this patient population.

If clinically necessary, a temporary peripheral IV cannula, preferably placed in a large vein, may be used for short term administration of study drug (Remodulin Package Insert). However, use of a peripheral IV infusion for more than a few hours may be associated with an increased risk of thrombophlebitis (Remodulin Package Insert).

Due to the inherent risks associated with central venous catheter placement, IV Remodulin was infused peripherally to healthy volunteers in two Phase I, open-label studies (16, 17). In the first study, Remodulin was diluted with 5% dextrose and administered to 15 subjects at a rate of 15ng/kg/minute for 150 minutes (17). No phlebitis was reported during the 150-minute peripheral IV infusion. The most common adverse events were headache (53%), dizziness (27%), and nausea (20%). In the second study, Remodulin was diluted with normal saline and administered to 53 subjects at 10ng/kg/minute for 3 days (16). This longer infusion was more problematic. Although no adverse events were judged to be serious, the most common adverse events involved the infusion site and included infusion site pain (57%), infusion site erythema (55%), infusion site edema (43%), and infusion site tenderness (13%). Other adverse events were mostly typical of prostacyclin administration, including: headache (53%), jaw pain (26%), and nausea (23%). Further analyses of these data to determine the optimal maximum duration of a peripheral infusion of Remodulin have not been conducted.

With any type of line, caution should be taken to ensure that:

1. No other drug or solution is co-administered through the line dedicated solely to study drug until notified by United Therapeutics of the outcome of the compatibility studies. Once compatibility with other IV agents has been confirmed, study drug may be administered in accordance with the data provided.
2. No blood specimens are drawn from the dedicated study drug line; this may lead to a temporary interruption in the study drug infusion.
3. The dedicated study drug line is **not flushed** as is standard nursing practice for most peripheral lines as flushing may lead to the delivery of a bolus dose.

Precautions should be taken to ensure that the study drug infusion continues uninterrupted.

Suggested precautions may include labeling the study drug lumen with warnings such as: "Do Not Stop," "Call MD Before Stopping," "Dedicated to study drug," "Do Not Flush," and/or "Do Not Draw Bloods."

In the event dedicated central venous access cannot be established, or in the opinion of the Investigator the patient is too unstable to attempt to establish a dedicated central venous access line for IV administration of study drug, study drug may be initiated as a continuous SC infusion at the discretion of the Investigator. Subjects initiated on IV administration of study drug who lose venous access may be transitioned to SC administration. Remodulin is bioequivalent between the SC and IV route, therefore no dose adjustment is needed if the SC route is utilized.

1 PREFACE

This plan provides further details of the planned analyses for the RIV-PN-201 study as presented in the study protocol. This plan, based on the original RIV-PN-201 study protocol dated 12 Aug 2013 and the subsequent study protocol amendments (latest version study protocol amendment 3 dated 15 Apr 2016), provides further details of the planned analyses stated in the study protocol and any additional planned analyses. Additional post-hoc or unplanned analyses that are not defined in this Statistical Analysis Plan (SAP) may be performed. Such analyses will be documented in the Clinical Study Report (CSR).

2 STUDY OBJECTIVES AND ENDPOINTS

The primary study objective is to explore the safety and treatment effect of intravenous (IV) Remodulin as add-on therapy in neonates with persistent pulmonary hypertension of the newborn (PPHN) compared to placebo. A secondary objective is to evaluate treprostinil pharmacokinetics (PK) in neonates with PPHN.

2.1 PRIMARY ENDPOINT

The primary endpoint is the composite endpoint of clinical worsening through Day 14 as defined by one of the following:

- Death
- Initiation of extracorporeal mechanical oxygenation (ECMO) per institutional policies
- Need for additional treatment (initiation of an additional targeted pulmonary vasodilator therapy [eg, phosphodiesterase type 5 inhibitor {PDE-5I}, endothelin receptor antagonist {ERA}, prostanoid, L-citrulline}]

2.2 SECONDARY ENDPOINTS

The secondary endpoints are as follows:

- Change in oxygenation index (OI) from Baseline to Hours 12, 24, and 72, and Days 7 and 14 and/or prior to study drug discontinuation/weaning
- Change in partial pressure of oxygen saturation (PaO₂)/fraction of inspired oxygen (FiO₂) (P/F ratio) from Baseline to Hours 12, 24, and 72
- Change in pre- and post-ductal saturation of peripheral capillary oxygenation (SpO₂) from Baseline to Hours 6, 12, 24, and 72
- Time to discontinuation of inhaled nitric oxide (iNO)
- Time on mechanical ventilation

- Time to initiation of ECMO
- Time to clinical worsening
- Change in N-terminal pro-brain natriuretic peptide (NT-proBNP)

2.3 SAFETY ENDPOINTS

Safety endpoints are as follows:

- Adverse events (AEs)
- Clinical laboratory parameters
- Physical examinations

3 STUDY DESIGN

This is a randomized, double-blind, placebo-controlled, multi-center, comparative study that will enroll neonates in the intensive care unit (ICU) with PPHN. Eligible subjects must have 2 consecutive OIs of 15 or greater, separated by at least 30 minutes, after having received iNO for at least 3 hours. Once enrolled, subjects will be randomized to receive Remodulin (treprostinil) or placebo.

This study is designed to evaluate the treatment effect of Remodulin as add-on therapy compared to placebo during a 14-day treatment period. However, to assess continued safety in this neonatal population, subjects with residual or chronic pulmonary hypertension (PH) that does not fully resolve within 14 days may continue to receive study drug for up to an additional 14 days (up to 28 days total) per the Investigator's discretion. Post-treatment data will be collected until death, time of hospital discharge, time of withdrawal from study, or for 4 weeks after last dose of study drug, whichever comes first. Subjects with ongoing AEs at the time of hospital discharge will continue to be followed for their AEs until either resolution (or return to normal or Baseline values), until judged by the Investigator to no longer be clinically significant, or until 4 weeks after last dose of study drug. All serious adverse events (SAEs) should be followed until resolution, death, or the subject is lost to follow-up, even if they are ongoing for more than 4 weeks after last dose of study drug.

4 SEQUENCE OF PLANNED ANALYSES

Interim Safety Analyses

A safety review will be conducted by a Data Safety Monitoring Board (DSMB) after the first 10 subjects have been randomized to receive study drug and have completed the 14-day treatment period. A second review will occur once 40 subjects have been enrolled and completed the 14-day treatment period. Ad hoc meetings may be scheduled at additional enrollment milestones or in response to events related to the safety of study treatment.

Interim Efficacy and Futility Analyses

Efficacy and futility will be assessed at the second formal data review. Details of the planned analyses and stopping rules are specified in the DSMB SAP. If the DSMB votes to stop the study at the second review, all analyses will be conducted as specified in this SAP on the 40 available subjects. Otherwise, these analyses will not be conducted until the study is completely enrolled.

Final Analysis after Database Lock and Study Unblinding

After the database has been quality assured and locked, the treatment assignments will be provided to the Sponsor's project statistician by the central randomization service and all planned analyses described in this document will be performed. By intent, no changes will be made to the clinical database after unblinding. However, any changes that are deemed necessary, after unblinding, will be clearly documented in the CSR.

5 SAMPLE SIZE CONSIDERATIONS

Based on the systematic review of use of nitric oxide for respiratory failure in infants by Finer and Barrington (2006), 57.9% (194/335) subjects in the control group had an outcome of death or requirement for ECMO (Finer 2006). In this study, assuming 60% of subjects in the placebo group and 30% of subjects in the Remodulin group with an outcome of death, requirement for ECMO, or need for additional PH therapy, we calculated that 66 subjects (33 subjects per treatment group) will have at least 80% power to show a significant difference in favor of Remodulin at alpha level 0.05 (1-sided test). Approximately 70 subjects are planned to be

randomized (1:1) to either receive treatment with Remodulin or placebo in addition to the standard of care.

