- Post-treatment data will be collected until subject is withdrawn from the study, death, time of hospital discharge, or until 4 weeks after last dose of study drug, whichever comes first.
 - The following key assessments will occur at time of withdrawal from study, hospital discharge, or at 4 weeks after last dose of study drug, whichever comes first: physical exam, vital signs, and clinical laboratory assessments.
 - Additionally, time on mechanical ventilation, time on inhaled iNO, and time of initiation of EMCO (if applicable) will be recorded.
 - The subject's participation in the study will conclude at the time of hospital discharge, death, withdrawal from the study, or at 4 weeks after last dose of study drug, whichever comes first.
 - Subjects with ongoing AEs at the time of study withdrawal or hospital discharge will continue to be followed for their AEs until either resolution (or return to normal or Baseline values), until judged by the Investigator to no longer be clinically significant, or until 4 weeks after last dose of study drug. All SAEs will be followed until resolution, death, or the subject is lost to follow-up, even if they are ongoing more than 4 weeks after the last dose of study drug.

Statistical Considerations	Based on the systematic review of use of nitric oxide for respiratory failure in infants by Finer and Barrington, 57.9% (194/335) subjects in the control group had an outcome of death or requirement for EMCO. In this study, assuming 60% subjects in placebo group and 30% subjects in Remodulin group with an outcome of death, requirement for EMCO, or need for additional PAH therapy, we calculated that 66 subjects (33 subjects per treatment group) will have at least 80% power to show a significant difference in favor of Remodulin at alpha level of 0.05 (one-sided test).
-----------------------------------	--

Approximately seventy subjects are planned to be randomized (1:1) to either receive treatment with Remodulin or placebo on top of the standard of care.

Sponsor United Therapeutics Corp.
 [name]
 [name]
 [name]

TABLE OF CONTENTS

LIST OF CONTACTS FOR STUDY	2
INVESTIGATOR'S AGREEMENT	3
PROTOCOL SYNOPSIS	4
TABLE OF CONTENTS.....	10
Table of In-text Tables.....	14
Table of In-text Figures	14
LIST OF ABBREVIATIONS	15
1 BACKGROUND AND RATIONALE	17
1.1 DEFINITION OF CLINICAL PROBLEM.....	17
1.2 REMODULIN (TREPROSTINIL) BACKGROUND	18

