10.2 SAMPLE SIZE

Based on the systematic review of use of nitric oxide for respiratory failure in infants by Finer and Barrington, 57.9% (194/335) subjects in control group had an outcome of death or requirement for EMCO (18). In this study, assuming 60% subjects in placebo group and 30% subjects in Remodulin group with an outcome of death, requirement for EMCO, or need for additional PAH therapy, we calculated that 66 subjects (33 subjects per treatment group) will have at least 80%

power to show a significant difference in favor of Remodulin at alpha level of 0.05 (one-sided test). Approximately 70 subjects are planned to be randomized (1:1) to either receive treatment with Remodulin or placebo on top of the standard of care.

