10.3 ANALYSIS PLAN

10.3.1 Primary Endpoint

Efficacy analyses will be performed in intention to treatment (ITT) population where ITT population includes all randomized subjects who have successfully initiated the study treatment.

The primary endpoint is clinical worsening (need for additional treatment [initiation of another targeted pulmonary vasodilator therapy], initiation of ECMO or death) between Baseline and Day 14 or time of discharge from the hospital, whichever comes first. It will be analyzed as a binary endpoint using the percentage of subjects who meet the definition of clinical worsening within each treatment group. Subjects who meet the definition of clinical worsening after Day 14 will not be counted towards the primary endpoint. Chi-square test will be used to test for the treatment difference.

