8 GENERAL CONSIDERATIONS FOR DATA ANALYSES

All the data collected in the electronic Case Report Form (eCRF) will be listed. In general, listings will be sorted by treatment group, subject number, and scheduled assessment (if applicable). Listings will include assessment date, assessment time (if available), study day, and all relevant data collected in the eCRFs. For data collected on a fixed schedule, the assessment identifier or the nominal time point will also be included on the listing. Repeat or redundant observations within an assessment window and observations that do not fall within any predefined assessment window (and will, therefore, be excluded from summaries) will be flagged in these listings. Subjects who are not to be included in the analysis population (eg, Safety population, Per Protocol population) will be flagged.

In general, the data will be summarized by scheduled assessment (if applicable) within each treatment group. For continuous variables, summary statistics will include the mean, standard deviation, median, minimum, and maximum. For summaries of non-normal data, interquartile range (lower quartile, upper quartile) may also be included. Minimums and maximums will be expressed using the level of precision in which the variable was collected. All other statistics will be rounded, using an additional decimal place than was collected. For discrete variables, summaries will include the frequency and percentage in each category. Percentages will be rounded to 1 decimal place. For all inferential analyses and descriptive comparisons, p-values will be rounded to 4 decimal places. Values less than 0.0001 will be denoted as <0.0001, and values greater than 0.9999 will be denoted as >0.9999 whenever practical. Categories of discrete variables will be ordered and labelled as they appear in the eCRF, and all categories represented on the eCRF will be included in summaries, even when they do not apply to any subjects in the study.

Unless otherwise specified, all statistical tests will be 2-sided at alpha level 0.05. All statistical calculations will be completed using the SAS® Version 9.4 or above.

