8.4 MULTIPLE COMPARISONS AND MULTIPLICITY

The primary efficacy endpoint of clinical worsening through Day 14 will be tested at alpha level 0.05. If the primary efficacy endpoint is statistically significant at alpha level 0.05, the statistical tests for secondary efficacy endpoints will be performed. As these comparisons are exploratory, no adjustments for multiplicity are planned.

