10.1.1.2 Primary Efficacy Analysis

The frequency and percentage of subjects who experience clinical worsening through Day 14 will be calculated for each treatment group. A chi-square test will be conducted to compare the incidence of clinical worsening between the treprostinil and placebo treatment groups.

The SAS Procedure FREQ will be used. The pseudo SAS statements are listed below:

```
proc freq;
  tables Treatment* Worsening / chisq;
run;
```

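### The stated power of at least 80% belongs to a one-sided 0.05 test; the two-sided 0.05 test in the SAP has about 70% power at 33 per arm

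*SAP*

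**What the plan says.** **Sample-size text (one-sided).** Assuming clinical worsening in 60% on placebo and 30% on Remodulin, the protocol synopsis says that 33 subjects per group "will have at least 80% power to show a significant difference in favor of Remodulin at alpha level of 0.05 (one-sided test"). Protocol section 10.2 repeats this: "power to show a significant difference in favor of Remodulin at alpha level of 0.05 (one-sided test"). SAP section 5 carries it over: 33 subjects per group "will have at least 80% power to show a significant difference in favor of Remodulin at alpha level 0.05 (1-sided test").

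**Analysis text (two-sided, or silent).**

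- SAP section 8: "Unless otherwise specified, all statistical tests will be 2-sided at alpha level 0.05".
- SAP section 10.1.1.1: the alternative for the primary endpoint is p1 ≠ p2.
- SAP section 10.1.1.2: "A chi-square test will be conducted to compare the incidence of clinical worsening between the treprostinil and placebo treatment groups". The code is PROC FREQ with the chisq option, which is non-directional.
- SAP section 8.4: "The primary efficacy endpoint of clinical worsening through Day 14 will be tested at alpha level 0.05". No side is given.
- Protocol section 10.3.1: "Chi-square test will be used to test for the treatment difference". Again no side is given.

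**What depends on the result.** SAP section 8.4 continues: "If the primary efficacy endpoint is statistically significant at alpha level 0.05, the statistical tests for secondary efficacy endpoints will be performed". SAP section 10.1.1.3 likewise makes the per-protocol analysis and the analysis by CDH status conditional on a significant primary result.

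**The concern.** The power statement describes a test that the SAP does not plan to run, and nothing in either document says that the chi-square p-value will be halved or read in one direction. Two things follow.

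First, a non-significant two-sided result would be interpreted as coming from a trial with 80% power, when the planned test has appreciably less.

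Second, the same data can succeed under one text and fail under the other. Because the primary result decides whether the secondary tests and the supporting analyses are run, the disagreement spreads beyond one p-value. If both readings are still open at unblinding, the choice between them could be made with the data in view.

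**Working it through.** **Inputs.** Event rates 60% and 30%, 33 per arm, alpha 0.05 (SAP section 5, protocol section 10.2). Allocation is 1:1 (protocol section 5.1). About 70 subjects are to be randomized, which is 35 per arm. The mean rate is (0.60 + 0.30)/2 = 0.45.

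**Formula.** Normal approximation with pooled variance under the null and no continuity correction:

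Power = Φ{[0.30 − z × √(2 × 0.45 × 0.55/n)] / √[(0.24 + 0.21)/n]}

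**The plan's own figure.** For n = 33 the null standard error is √(0.495/33) = 0.1225 and the alternative standard error is √(0.45/33) = 0.1168. With z = 1.645 (one-sided 0.05): (0.30 − 0.2015)/0.1168 = 0.844, so power is 80.1%. The stated figure and the 33 per arm both reproduce.

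**The SAP's test.** Change only z to 1.960 (two-sided 0.05):

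| n per arm | One-sided 0.05 | Two-sided 0.05 |
|---|---|---|
| 33 | 80.1% | 69.6% |
| 34 | – | 71.0% |
| 35 | 82.1% | 72.2% |

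At n = 33 the two-sided step is (0.30 − 0.2400)/0.1168 = 0.513, so power is 69.6%. The like-for-like loss is 80.1 − 69.6 = 10.5 points.

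**Check by exact binomial enumeration** of the uncorrected Pearson chi-square, two-sided 0.05:

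- Over near-even splits of 66 to 70 subjects, power runs from 69.2% (33 placebo, 35 Remodulin) to 73.6% (33:33). At 35:35 it is 70.8%.
- At 33:33 the one-sided power is 81.2%, so the exact loss there is 81.2 − 73.6 = 7.6 points.
- The 73.6% is flattered by the test's size: at 33:33 its true two-sided size is 0.063 when both rates are 0.45.

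**Other variants, two-sided, 33 per arm.** Unpooled variance 72.9%, arcsine 70.2%, continuity-corrected 60.0%, Fisher's exact test 64.6%. The highest two-sided figure from any variant at 33 or 35 per arm is 75.4% (unpooled, 35 per arm).

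**Do the two criteria disagree on real tables?**

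| Placebo | Remodulin | Two-sided p | One-sided p |
|---|---|---|---|
| 20/33 | 13/33 | 0.085 | 0.042 |
| 21/35 | 14/35 | 0.094 | 0.047 |
| 21/35 | 13/35 | 0.056 | 0.028 |

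For the first row the pooled rate is 33/66 = 0.5, the standard error is √(2 × 0.25/33) = 0.1231, and Z = (7/33)/0.1231 = 1.72. With 20/33 placebo events, the one-sided test accepts up to 13 Remodulin events and the two-sided test up to 12. With 21/35, the limits are 14 and 12.

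**How often?** Under 60% versus 30%, the exact probability of passing one-sided and failing two-sided is 7.6% at 33:33. At 35:35 it is 84.3% − 70.8% = 13.6% (from unrounded values).

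**The case against.** The strongest reply is that there is really one decision rule. The one-sided wording appears only in sample-size paragraphs, the SAP's analysis sections consistently point to a two-sided test, and the section 8 default fills the gap in section 8.4. On that reading the 80% is a correct calculation for the test it names. This is partly right: the arithmetic is sound and the fault is an inconsistency. But the protocol mentions only a one-sided test and SAP section 5 repeats it, so the power claim is wrong for the planned test on any reading. Nor can section 5 be the exception that section 8 allows for, because section 10.1.1.1 then contradicts it.

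Three further points have some force:

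- **The 70% depends on the approximation.** Exact power at 33:33 is 73.6%, so 70% to 74% is a fair range for that design. All of it is well below 80%.
- **There are other ways to reconcile.** The sponsor could declare the primary test one-sided throughout, or enlarge the trial. Either would also remove the contradiction.
- **The study is Phase II and its objective is to explore.** The SAP nevertheless sets a formal hypothesis, an alpha level and a gate, so the criterion has to be unambiguous.

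**Conclusion.** The concern holds. The stated power of at least 80% is for a test that the SAP does not specify. For the two-sided 0.05 chi-square that it does specify, power at 60% versus 30% is about 70% with 66 subjects and about 71% to 72% if all 70 are analysed. The two texts would give different verdicts on the primary endpoint with probability 7.6% at 33 per arm and 13.6% at 35 per arm, under the plan's own assumptions.

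These figures assume that the planned event rates are true, that the chi-square is uncorrected, and that there is a single look. SAP section 4 plans an efficacy and futility assessment at the second data review, with 40 subjects. Its rules are in a separate DSMB SAP that is not among these documents, and they could change the final power.

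**What to change.** Keep the two-sided 0.05 test that SAP sections 8, 10.1.1.1 and 10.1.1.2 already define, and make the rest agree with it:

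1. In the protocol synopsis, protocol section 10.2 and SAP section 5, replace the one-sided power statement with: *66 subjects (33 per group) give about 70% power to detect 60% versus 30% at a two-sided alpha of 0.05.* Say that this is a single-look, normal-approximation figure.
2. Add the word two-sided to the primary test in protocol section 10.3.1 and SAP section 8.4, so that one criterion governs the primary result and everything it gates.

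The cost is wording in five places and a less favourable stated power. The test, sample size and conduct do not change.

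If the sponsor is not content with about 70%, the same formula gives 80.0% two-sided power at 42 per arm (84 evaluable subjects). That is a design decision and not a correction of wording. Declaring the primary test one-sided would need matching changes to SAP sections 8.4, 10.1.1.1 and 10.1.1.2 before unblinding.
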